## **6.0 DETERMINATION OF SAMPLE SIZE**

A total of 14 subjects (7 per sequence)

In case an add-on subject study is conducted, the maximum number of subjects will be 120 (60 per sequence).

[Rationale for the sample size]

Based on the currently available results of the studies conducted to date, the residual sum of squares of pharmacokinetic parameters  $C_{max}$  and  $AUC_{48}$  in the present study was assumed to be 0.13 and 0.08, respectively. For 6 subjects per sequence (total of 12 subjects per formulation), in two one-sided t-tests [ $H_0: \ln(\mu) \leq \ln(\theta_1), \ln(\mu) \geq \ln(\theta_2)$ ;  $H_1: \ln(\theta_1) < \ln(\mu) < \ln(\theta_2)$ ; where  $\mu = \mu_t / \mu_s$ ,  $\mu_t$  was the population mean for the pediatric formulation  $\mu_s$  was the population mean for the TAK-536 commercial formulation,  $\theta_1 = 0.80$ , and  $\theta_2 = 1.25$ ] with a one-sided significance level of 5% and alternative hypothesis  $\mu = 0.95$ , more than 90% power of simultaneous detection of the bio-equivalence for pharmacokinetic parameters  $C_{max}$  and  $AUC_{48}$ . Taking into account possible occurrence of dropouts during the study and feasibility, 7 subjects per sequence (total of 14 subjects per formulation) were set.

In case bio-equivalence cannot be demonstrated with the number of subjects initially planned on account of insufficient subjects, an add-on subject study will be conducted in accordance with the Guideline for Bioequivalence Studies of Generic Products [1]. The maximum number of subjects in the add-on subject study is 120 (60 per sequence), which is determined based on study feasibility, but is not on statistical consideration. The number of subjects in the add-on subject study will be determined based on the result of the interim analysis in this study and the currently available results of the studies conducted to date.

## 7.0 METHODS OF ANALYSIS AND PRESENTATION

### 7.1 General Principles

#### 7.1.1 Study Definitions

- Treatment-emergent adverse event (TEAE): Adverse events that occurred after the start of the study drug administration
  - \* Among the TEAEs, those that occurred from the start of the study drug administration in Period 1 to before the start of the study drug administration in Period 2 are deemed as “TEAEs that occurred in Period 1” and those that occurred after the start of the study drug administration in Period 2 as “TEAEs that occurred in Period 2.”
- Pretreatment event(PTE):Adverse events that occurred after obtaining the consent but before the start of the study drug administration
- Descriptive statistics: Number of subjects, mean, standard deviation, maximum, minimum, and quartiles
- Coefficient of variation (CV)(%): Standard deviation / Mean x 100
- QTcF interval: QT interval corrected with Fridericia’s correction
- Formulations:
  - TAK-536 commercial formulation
  - TAK-536 pediatric formulation
- Treatment group:
  - a (TAK-536 pediatric formulation→TAK-536 commercial formulation)
  - b (TAK-536 commercial formulation→TAK-536 pediatric formulation)

#### 7.1.2 Definition of Study Days

- Total Study Time in each time interval (hour): Time and date of test/observation/assessment - Time and date of start of study drug administration in each time interval (rounded to the fourth decimal place)

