	0.5, 1, 1.5, 2, 2.5, 3, 3.5, 4, 5, 6, 8, and 12 hours postdose	±5 minutes
	16, 24, and 48 hours postdose	±15 minutes

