#### 7.1.3 Definition of Study Visit Windows

For items of examinations, observations, and assessments described below, evaluable data (i.e., non-missing data) will be handled according to the following rules.

Evaluable data within the visit window will be used. If more than one evaluable data exist within the same visit window, the examinations, observations, and assessments with the closest Study Time to the scheduled Study Time will be used. If there are two evaluable equidistant to the scheduled Study Time, the later data will be used. The size of difference from the Study Time will be determined based on the total Study Time in each time interval (hour) .

For items from examinations, observations, and assessments other than those described below, evaluable data will be handled as data at the corresponding visit based on the visits specified in the case report form. However, among the visits specified in the case report form, if the follow-up examination in Period 1 (Day 6) and the examination on the day before the study drug administration (Day -1) in Period 2 were conducted on the same day and only the evaluable data exists from either the follow-up examination (Day 6) for Period 1 or the day before the study drug administration (Day -1) for Period 2, that data will be handled though it were obtained at both visits.

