**Table 7.a Visit Window**

Plasma drug concentration

Visit	Scheduled Study Time	Total Study Time in each time interval (hour)
Predose	Study Time (hour): 0	-5.000 - 0.000
0.5 Hour Postdose	Study Time (hour): 0.5	0.417 - 0.583
1 Hour Postdose	Study Time (hour): 1	0.917 - 1.083
1.5 Hours Postdose	Study Time (hour): 1.5	1.417 - 1.583
2 Hours Postdose	Study Time (hour): 2	1.917 - 2.083
2.5 Hours Postdose	Study Time (hour): 2.5	2.417 - 2.583
3 Hours Postdose	Study Time (hour): 3	2.917 - 3.083
3.5 Hours Postdose	Study Time (hour): 3.5	3.417 - 3.583
4 Hours Postdose	Study Time (hour): 4	3.917 - 4.083
5 Hours Postdose	Study Time (hour): 5	4.917 - 5.083
6 Hours Postdose	Study Time (hour): 6	5.917 - 6.083
8 Hours Postdose	Study Time (hour): 8	7.917 - 8.083
12 Hours Postdose	Study Time (hour): 12	11.917 - 12.083
16 Hours Postdose	Study Time (hour): 16	15.750 - 16.250
24 Hours Postdose	Study Time (hour): 24	23.750 - 24.250
48 Hours Postdose	Study Time (hour): 48	47.750 - 48.250

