## **7.2 Analysis Sets**

- Pharmacokinetic (PK) Analysis Set: All subjects who received the study drug, completed the minimum protocol-specified procedures without any major protocol deviations, and were evaluable for pharmacokinetics
  - Any subject who meets the following criteria will be excluded from this analysis set:
    - 1) Deviations of protocol entry criteria
      - Deviations of inclusion criteria
        - Inclusion criteria 3, 4, and 5
        - Deviations of exclusion criteria
          - Exclusion criteria 2, 4, 6, 7, 8, 9, 10, 11, and 17

- 2) Deviations related to treatment procedure or dose
  - Deviations related to dose
    - Deviations of dosage

Subjects who received a dose of the study drug other than the doses specified in the protocol
    - Deviations of regimen

Deviations of dosing interval (number of days for washout)  
Subjects who received the study drug in Period 2 without undergoing a washout period of more than 6 days after the study drug administration in Period 1
    - Deviations of dosing conditions

Subjects who did not orally receive a single dose of any study drug under fasted conditions in the morning (fasted for more than 10 hours before the study drug administration)
- 3) Deviations concerning excluded medication or therapy
  - Deviations concerning concomitant medications
    - Administration of excluded medication

Subjects who consumed drugs (prescribed or over-the-counter drugs) described in Table 7. a “Prohibited Medications, Supplements, Dietary Products or Food Products” of the protocol’s section 7.3 within the given time
- 4) Deviations concerning pharmacokinetic measurements
  - Plasma drug concentration
    - No conduct/missing of examinations and assessments concerning pharmacokinetic variables

Subjects whose plasma drug concentration data of TAK-536 was missing or not used at more than 1 visit
- 5) Others
  - Matters of subject management
    - Matters concerning foods and beverages

Subjects who consumed meals other than the provided meals during hospitalization

Subjects who consumed meals within 10 hours before the study drug administration

Subjects who consumed meals within 4 hours after the study drug administration

Subjects who consumed beverages other than water (200 mL) with the study drug from 1 hour before to 4 hours after the study drug administration

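### Read literally, the SAP's four-decimal study time and three-decimal window limits put a 0.5 to 12 h PK sample taken exactly 5 minutes off schedule outside the SAP window, although the protocol accepts it; the rounding rule needs clarifying.

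*SAP*

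**What the plan says.** **Protocol window.** Protocol Appendix A (acceptable time windows, pharmacokinetics) allows ±5 minutes for the samples at "0.5, 1, 1.5, 2, 2.5, 3, 3.5, 4, 5, 6, 8, and 12 hours postdose", and ±15 minutes at 16, 24 and 48 h.

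**Study time.** SAP 7.1.2 defines total study time as the date and time of the assessment minus the date and time of the "start of study drug administration in each time interval (rounded to the fourth decimal place"). The interim SAP repeats this.

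**SAP window.** Table 7.a, in both SAPs, lists the limits under the name of that same variable. Every limit has three decimals, for example "11.917 - 12.083" at 12 h and "15.750 - 16.250" at 16 h. SAP 7.1.3 then says: "Evaluable data within the visit window will be used". It gives no tolerance for a sample on a limit.

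**Consequence.** SAP 7.2 item 4 removes from the PK analysis set any subject whose TAK-536 concentration "was missing or not used at more than 1 visit". In Table 7.a each sampling time is a visit.

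**The concern.** Five minutes is one twelfth of an hour, a recurring decimal. Rounding it to three places for the table moves every ±5 minute limit slightly inward. A study time held to four places is then compared with a limit that is slightly too tight. A sample on the last permitted minute complies with the protocol, yet the SAP as worded does not use it.

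The primary bioequivalence analysis is run on the PK analysis set. The study plans 14 subjects, its power statement rests on 12, and subjects who drop out after dosing in Period 1 are not replaced (Protocol 7.6). The same wording is in the interim SAP, whose analysis informs the decision on an add-on study. A subject could therefore leave the primary analysis without any protocol deviation, because of a rounding convention.

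**Working it through.** **Inputs.** Protocol Appendix A: ±5 min at 12 time points (0.5 to 12 h), ±15 min at 16, 24 and 48 h. SAP 7.1.2: the rounding rule. SAP Table 7.a: the limits, taken as inclusive. SAP 7.2 item 4: exclusion when more than one visit is missing or not used.

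**Step 1: reproduce Table 7.a.** Limit = scheduled time ± 5/60 h (or ± 15/60 h), rounded to three decimals.
- 0.5 h: 0.5 − 0.08333 = 0.41667, giving 0.417; 0.5 + 0.08333 = 0.58333, giving 0.583.
- 12 h: 11.91667 gives 11.917; 12.08333 gives 12.083.
- 16 h: 15.750 and 16.250, exact.

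All 15 postdose windows reproduce this way.

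**Step 2: compare samples exactly on the protocol edge.**

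| Study time held as | 5 min early at 0.5 h | 5 min late at 0.5 h | Edges inside, 0.5 to 12 h |
|---|---|---|---|
| four decimals | 0.4167 < 0.417, outside | 0.5833 > 0.583, outside | 0 of 24 |
| unrounded | outside | outside | 0 of 24 |
| truncated to three decimals | 0.416, outside | 0.583, inside | 12 of 24 |
| rounded to three decimals | 0.417, inside | 0.583, inside | 24 of 24 |

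The 24 edges are 12 time points × 2 sides. The gap is (0.417 − 0.416667) × 3600 = 1.2 seconds. A sample 4 minutes off is inside at all 12 time points (at 0.5 h: 0.4333 and 0.5667). At 16, 24 and 48 h a sample exactly 15 minutes off lies on the limit and is inside under every variant.

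**Step 3: chance that a compliant subject is excluded.** Let p be the share of samples from 0.5 to 12 h recorded exactly 5 minutes off. The documents give no value for p, so a range is shown. Assume independent samples, times recorded to the minute, and no other missing sample. Each subject has 12 × 2 = 24 such samples.

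- Counted across both periods: P = 1 − (1 − p)^24 − 24p(1 − p)^23.
- Counted within a period: q = 1 − (1 − p)^12 − 12p(1 − p)^11, and P = 1 − (1 − q)^2.

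Example, p = 1%, across both periods: 1 − 0.7857 − 0.1905 = 0.0239. Multiplying the unrounded value by 14 gives 0.33 expected subjects.

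| p | Across both periods | Expected of 14 | Within a period | Expected of 14 |
|---|---|---|---|---|
| 0.1% | 0.03% | 0.004 | 0.01% | 0.002 |
| 0.5% | 0.64% | 0.09 | 0.32% | 0.04 |
| 1% | 2.4% | 0.33 | 1.2% | 0.17 |
| 2% | 8.3% | 1.2 | 4.6% | 0.64 |

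**The case against.** The strongest reply is that the rounding phrase can mean rounding at the fourth decimal, which leaves three. The table supports this. Its limits column carries the name of the variable defined in 7.1.2. Every entry is padded to three places even where that is unnecessary (−5.000, 0.000, 15.750). The limits are what such rounding would produce. On that reading all 24 edges are inside and nothing is lost. This stands as a plausible account of the intent. It does not settle the matter, because the text never says it and a programmer following the words literally would keep four decimals.

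Three stronger readings are tempting, and the documents do not support them.

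- A reader might infer that the plan certainly rejects these samples. It does so only on the literal reading.
- A reader might infer that any PK sample 5 minutes off is affected. At 16, 24 and 48 h it is well inside ±15 minutes. Nor do the documents place all 12 affected time points near Cmax, since they run to 12 h.
- A reader might infer a large loss of subjects. With p = 5% the same formula gives 34% per subject, or 4.7 of 14, but that needs one sample in twenty to sit exactly on the last permitted minute. Nothing in the documents supports such a figure.

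It is also fair to say that one unused sample excludes nobody, that the SAP does not state whether visits are counted within a period or across both, and that Protocol 9.1.10.1 requires the actual time to be recorded without giving its resolution. If seconds are kept, only a strip of about 1.2 seconds at each edge is affected.

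**Conclusion.** The point holds as an ambiguity with a definite consequence on its literal reading. SAP 7.1.2 and Table 7.a do not clearly use the same precision. If four decimals are kept, a sample exactly on the ±5 minute edge at 0.5 to 12 h complies with the protocol and is not used, and more than one removes the subject from the PK analysis set. If three decimals were meant, there is no mismatch.

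The likely effect is small. The chance per subject runs from about 0.03% (p = 0.1%) to 8.3% (p = 2%) counted across both periods, and about half that within a period. This rests on an unknown p, on independence and on minute-level recording. Severity is low. The reason to act is that which samples enter the primary analysis of an open-label study should not depend on how a phrase is read once data are available.

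**What to change.** Make one of two changes, in both the final and the interim SAP, before the interim database lock:

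- state in 7.1.2 that study time is rounded (not truncated) to three decimal places, the precision of Table 7.a; or
- define the postdose windows in Table 7.a in whole minutes: scheduled time ±5 min for 0.5 to 12 h and ±15 min for 16, 24 and 48 h, limits included.

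Either one reproduces the protocol's own windows and brings all 24 edge cases inside. The cost is one line of wording in each SAP. There is no evident downside, and no sampling time or clinical procedure changes.

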#### 7.1.3 Definition of Study Visit Windows

For items of examinations, observations, and assessments described below, evaluable data (i.e., non-missing data) will be handled according to the following rules.

Evaluable data within the visit window will be used. If more than one evaluable data exist within the same visit window, the examinations, observations, and assessments with the closest Study Time to the scheduled Study Time will be used. If there are two evaluable equidistant to the scheduled Study Time, the later data will be used. The size of difference from the Study Time will be determined based on the total Study Time in each time interval (hour) .

For items from examinations, observations, and assessments other than those described below, evaluable data will be handled as data at the corresponding visit based on the visits specified in the case report form. However, among the visits specified in the case report form, if the follow-up examination in Period 1 (Day 6) and the examination on the day before the study drug administration (Day -1) in Period 2 were conducted on the same day and only the evaluable data exists from either the follow-up examination (Day 6) for Period 1 or the day before the study drug administration (Day -1) for Period 2, that data will be handled though it were obtained at both visits.

**Table 7.a Visit Window**

Plasma drug concentration

Visit	Scheduled Study Time	Total Study Time in each time interval (hour)
Predose	Study Time (hour): 0	-5.000 - 0.000
0.5 Hour Postdose	Study Time (hour): 0.5	0.417 - 0.583
1 Hour Postdose	Study Time (hour): 1	0.917 - 1.083
1.5 Hours Postdose	Study Time (hour): 1.5	1.417 - 1.583
2 Hours Postdose	Study Time (hour): 2	1.917 - 2.083
2.5 Hours Postdose	Study Time (hour): 2.5	2.417 - 2.583
3 Hours Postdose	Study Time (hour): 3	2.917 - 3.083
3.5 Hours Postdose	Study Time (hour): 3.5	3.417 - 3.583
4 Hours Postdose	Study Time (hour): 4	3.917 - 4.083
5 Hours Postdose	Study Time (hour): 5	4.917 - 5.083
6 Hours Postdose	Study Time (hour): 6	5.917 - 6.083
8 Hours Postdose	Study Time (hour): 8	7.917 - 8.083
12 Hours Postdose	Study Time (hour): 12	11.917 - 12.083
16 Hours Postdose	Study Time (hour): 16	15.750 - 16.250
24 Hours Postdose	Study Time (hour): 24	23.750 - 24.250
48 Hours Postdose	Study Time (hour): 48	47.750 - 48.250

## **7.2 Analysis Sets**

- Pharmacokinetic (PK) Analysis Set: All subjects who received the study drug, completed the minimum protocol-specified procedures without any major protocol deviations, and were evaluable for pharmacokinetics
  - Any subject who meets the following criteria will be excluded from this analysis set:
    - 1) Deviations of protocol entry criteria
      - Deviations of inclusion criteria
        - Inclusion criteria 3, 4, and 5
        - Deviations of exclusion criteria
          - Exclusion criteria 2, 4, 6, 7, 8, 9, 10, 11, and 17

- 2) Deviations related to treatment procedure or dose
  - Deviations related to dose
    - Deviations of dosage

Subjects who received a dose of the study drug other than the doses specified in the protocol
    - Deviations of regimen

Deviations of dosing interval (number of days for washout)  
Subjects who received the study drug in Period 2 without undergoing a washout period of more than 6 days after the study drug administration in Period 1
    - Deviations of dosing conditions

Subjects who did not orally receive a single dose of any study drug under fasted conditions in the morning (fasted for more than 10 hours before the study drug administration)
- 3) Deviations concerning excluded medication or therapy
  - Deviations concerning concomitant medications
    - Administration of excluded medication

Subjects who consumed drugs (prescribed or over-the-counter drugs) described in Table 7. a “Prohibited Medications, Supplements, Dietary Products or Food Products” of the protocol’s section 7.3 within the given time
- 4) Deviations concerning pharmacokinetic measurements
  - Plasma drug concentration
    - No conduct/missing of examinations and assessments concerning pharmacokinetic variables

Subjects whose plasma drug concentration data of TAK-536 was missing or not used at more than 1 visit
- 5) Others
  - Matters of subject management
    - Matters concerning foods and beverages

Subjects who consumed meals other than the provided meals during hospitalization

Subjects who consumed meals within 10 hours before the study drug administration

Subjects who consumed meals within 4 hours after the study drug administration

Subjects who consumed beverages other than water (200 mL) with the study drug from 1 hour before to 4 hours after the study drug administration

Subjects who consumed foods described in Table 7. a “Prohibited Medications, Supplements, Dietary Products or Food Products” of the protocol’s section 7.3 within the given time

Matters concerning smoking

Subjects who smoked during hospitalization

Matters concerning body position

Subjects who took a supine position for 4 hours after the study drug administration, unless it was required for examination.

- Safety Analysis Set: All subjects who received the study drug

